	Part 1 and	d Part 2:								

Formal statistical analysis will be performed on the PK parameters $AUC_{(0-t)}$, , $AUC_{(0-inf)}$ and C_{max} to assess dose proportionality using a power model approach, where t is 12 hours for Part 1 and 24 hours for Part 2.

This analysis will be performed for the following:

Part 1 (SAD): Day 1

Part 2 (MAD): Day 1 and Day 10 separately (assuming 3 or more dose levels are used).

Part 3:

Formal statistical analysis will be performed on the above PK parameters to assess relative bioavailability of ZP-059 to voriconazole. The PK parameters will undergo a natural logarithmic (loge) transformation and will be analysed using a mixed effects ANOVA. The mixed effects ANOVA model will include fixed effect terms for treatment, period, sequence and sex and a random effect term for subject (nested within sequence). Adjusted geometric mean ratio (GMR) and 90% confidence intervals (CIs) for the adjusted GMR for the comparison between test ZP-059 and reference oral voriconazole tablets will be provided, where the ratio is defined as test/reference.

In addition, the above PK parameters will be compared between asthma subjects in Part 3 and healthy subjects in Part 1 and separately with asthma subjects in Part 2 to assess relative bioavailability of the ZP-059 dose taken in Part 3 in these populations. An ANOVA model will be fitted to the loge transformed PK parameter including terms for the population group (i.e., healthy subjects or asthma subjects) and sex. The adjusted GMR and 90% CI for the adjusted GMR for the comparison between the two populations for the relevant dose will be provided, where the ratio is defined as either Part 3 subjects/Part 1 subjects or Part 3 subjects/Part 2 subjects, depending on the comparison.

Sample size calculation:

Part 1 (SAD - Healthy Subjects) and Part 2 (MAD - Mild, Stable Asthma Subjects):

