6.1. Administration of Investigational Products

Specific details of IMPs and doses to be administered are provided in Table 2 below. For all study parts, subjects will be dosed on each study period/dosing day, as applicable.

The exact time of dosing will be decided based on logistics and will be documented in the source records.

Subjects in Part 1 will receive a total of 1 administration of ZP-059 on one occasion. Subjects in Part 2 will receive a total of 10 administrations of ZP-059 on 10 separate occasions (based on the dosing frequency of q.d.) or in the event of BID dosing they will receive a total of 19 doses. Subjects in Part 3 will receive a total of 1 administration of ZP-059 on one occasion and a total of 1 administration of oral voriconazole (VFEND®) on one occasion.

Detailed instructions for dose administration will be provided in a pharmacy manual. The start and end time of dosing (i.e. first and last capsule dose times) will be recorded in the source data. For the purposes of PK sampling and post-dose procedures, the time of inhalation of the first capsule will be the dose time and thus time '0'.

For Part 3, the subjects will be required to swallow the VFEND® tablet whole with some water.

Table 3 Investigational Medicinal Products

Study Part	Cohort	IMP	Dose and Route of Administration	
1	SAD 1	ZP-059	5 mg (1 x 5 mg capsule) ZP-059 ^a Administered via DPI on Day 1	
	SAD 2	ZP-059	ZP-059 (Dose TBD) Administered via DPI on Day 1	
	SAD 3	ZP-059	ZP-059 (Dose TBD) Administered via DPI on Day 1	
	SAD 4	ZP-059	ZP-059 (Dose TBD) Administered via DPI on Day 1	
2	MAD 1	ZP-059	ZP-059 (Dose TBD) Administered via DPI once daily on Days 1 to 10 or twice daily on Days 1 to 9 and once on Day 10	
	MAD 2	ZP-059	ZP-059 (Dose TBD) Administered via DPI once daily on Days 1 to 10 or twice daily on Days 1 to 9 and once on Day 10	
	MAD 3	ZP-059	ZP-059 (Dose TBD) Administered via DPI once daily on Days 1 to 10 or twice daily on Days 1 to 9 and once on Day 10	
Study Part	Treatment Period	IMP	Dose and Route of Administration	
3	1 or 2	ZP-059	ZP-059 (Dose TBD) Administered via DPI on Day 1 of Period 1 or Period 2	
		Voriconazole (VFEND®) oral film-coated tablet	200 mg Voriconazole (VFEND® - oral film-coated tablet) on Day 1 of Period 1 or Period 2	

^a Fixed starting dose DPI; dry powder inhaler TBD; to be determined

Each capsule delivers 5 mg of voriconazole

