## 3.3 Study Design

This is an integrated Phase 1, single centre, multi-part, open-label study in both healthy subjects (Part 1), subjects with mild stable asthma (Part 2) and subjects with mild to moderate stable asthma (Part 3).

Part 1 is comprised of 4 separate cohorts containing 6 subjects each. Each subject will receive a single dose of ZP-059 with the dose increasing per cohort following review of safety data from the preceding cohort. The study will have an interleaved design. A further cohort may be enrolled if deemed appropriate to repeat a dose level, assess an interim dose or a dose higher than planned.

Part 2 is comprised of 3 separate cohorts containing 6 subjects each. The treatment period will be for 10 consecutive days with each subject receiving daily doses of ZP-059 (either once daily for 10 days, or twice daily for the first 9 days and once on Day 10), of which the dose and frequency is determined following a safety review of the data from Part 1 Cohort 2. Dose escalation in the next cohort will proceed following completion of the safety assessments 24 hours post dose on Day 10 for a minimum of 4 subjects. A further 2 cohorts may be enrolled if deemed appropriate to repeat a dose level, assess an interim dose, a different dosing regimen or a dose higher than planned.

Part 3 is a two period, randomised crossover study in 16 subjects with a minimum of 6 sputum producers and comprises of 2 cohorts to receive a single dose of ZP-059 in one period, of which the dose is determined following a safety review of the data from Part 1 (Cohorts 1 to 4), and a single dose of 200mg oral voriconazole in the other period. Subjects are randomised to the sequence in which they receive treatment. There will be a minimum wash out period of 96 hours between treatments. Dosing of Part 3 may occur prior to or in parallel with Part 2 of the study.

Further details of the study design can be found in section 4 of the protocol.

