#### 7.2.4 Treatment Start and End

Treatment start is defined as the first day of administration of study drug (Day 1) for Parts 1 & 2 of the study. For Part 3, Treatment start is defined as Day 1 of treatment period 1.

In Part 1 of the study, treatment is received as a single dose therefore treatment end is also Day 1.

For Part 2, treatment end is defined as the final day of administration of study drug which is scheduled as Day 10.

In Part 3, treatment is received as a single dose within the treatment period therefore treatment end is Day 1 of treatment period 2.

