#### 7.12.3 Dose proportionality

Dose proportionality of ZP-059 will be assessed by fitting a power model as follows:

$$log_{10}(y) = \alpha + \beta \ log_{10}(dose)$$

Where  $\alpha$  represents the random subject effects for intercept and dose. A value of 1 for  $\beta$  indicates perfect dose proportionality. Therefore, the estimate of  $\beta$  together with the corresponding 90% confidence interval (CI) will be used to quantify dose proportionality. The increase in concentration over the dose range will be estimated by the ratio of the expected concentration with the highest dose to that of the lowest dose. This will be derived by back-transforming the difference on the log10 scale between the two doses and will be accompanied by its associated 90% confidence interval. If the exposure is dose proportional there should be a fold increase equal to the ratio of highest: lowest dose across the dose range.

If it isn't possible to fit random subject slopes a common fixed effect slope will be fitted.

Dose proportionality will be assessed for each of the following PK endpoints for voriconazole and n-oxide voriconazole separately:

- Cmax
- AUC0-t, where t is 12 hours for Part 1, 24 hours for Part 2 and 96 hours for Part 3.
- AUC0-inf

These will be performed separately for Part 1 and Part 2 at Day 1 and Day 10. This analysis will be performed if 3 or more dose levels are used for the Part.

Dose proportionality will also be assessed using an analysis of variance (ANOVA) method. A mixed effects model will be fitted with fixed effects for dose and random effects for subject. The difference between the dose levels will be presented along with a 90% confidence interval and p-value.

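### SAP 7.12.3 gives the power model and the dose ANOVA random subject effects that one dose and one value per subject cannot support

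*SAP*

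**What the plan says.** SAP 7.12.3 fits log10(y) = α + β·log10(dose) and states that α "represents the random subject effects for intercept and dose". It reports β with a 90% CI, and the ratio of expected exposure at the highest dose to that at the lowest, also with a 90% CI. The fallback reads: "If it isn't possible to fit random subject slopes a common fixed effect slope will be fitted". A second method is an ANOVA: "A mixed effects model will be fitted with fixed effects for dose and random effects for subject". It gives differences between dose levels with 90% CIs and p-values.

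On the data entering each fit, SAP 7.12.3 says: "These will be performed separately for Part 1 and Part 2 at Day 1 and Day 10". The statistical methodology in the Protocol synopsis confirms that Part 2 Day 1 and Day 10 are separate analyses.

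On the design of Part 1, SAP 3.3 says: "Each subject will receive a single dose of ZP-059 with the dose increasing per cohort". Protocol 6.1 agrees: "Subjects in Part 1 will receive a total of 1 administration of ZP-059 on one occasion". In Part 2 the dose level is also set per cohort, and Protocol 5.2.2 excludes anyone who has already received study medication in this trial.

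Protocol 9.4.4.1 gives the same equation without any random term and plans no dose ANOVA. SAP section 2 lists one change from the protocol, the dropped linearity ratios. Neither document names a degrees-of-freedom method for these fits.

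**The concern.** A random subject intercept is separable from residual error only if subjects contribute repeated values. A random subject slope on dose is a within-subject quantity only if subjects receive more than one dose. Neither condition is met in any of the planned fits.

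Dose proportionality is the formal statistical analysis named for Parts 1 and 2, and β with its 90% CI is the stated measure. If the model cannot be estimated as written, the reported β and CI depend on choices that the SAP leaves open: the covariance structure, the optimiser, what counts as a fit that is not possible, and the df method. Two competent programmers could then publish different values from the same data.

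**Working it through.** The documents state no β, standard error (SE) or CI width for this analysis, so there is no figure to reproduce. The check is of identifiability, followed by an illustration of size.

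**Inputs from the documents.** Part 1: 4 × 6 = 24 subjects. Part 2: 3 × 6 = 18 subjects. One dose level per subject and one value per endpoint per fit. Starting dose 5 mg; single-dose ceiling 40 mg; 90% CI.

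**Assumptions, not from the documents.** Part 1 doses of 5, 10, 20 and 40 mg; true β = 1; SD 0.25 on the log10 scale.

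**1. Random intercept (dose ANOVA, and the fallback if it keeps one).** With one row per subject, the subject indicator matrix is the identity.
- The rank of fixed plus subject columns is 24 of 24 in Part 1 and 18 of 18 in Part 2, which leaves 0 residual df.
- Var(y) = σ²(subject) + σ²(residual) for every row, so only the sum can be estimated.
- In one illustrative Part 1 data set, the REML log-likelihood was 27.240599 with the subject share of the variance set at 0, 25, 50, 75 and 99.9%.
- At every split β was 0.945059 and its SE 0.096983, which are the ordinary least-squares values.

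**2. What could still move the CI under a random intercept.** Only the t multiplier. With 22 df the half-width is 1.717 × 0.096983 = 0.167. With infinite df it is 1.645 × 0.096983 = 0.160 (ratio 0.96). At 2 df the ratio would be 1.70, and at 1 df 3.68.

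**3. Random intercept plus random slope (the first choice).** With x = log10(dose), Var(y | x) = s00 + 2·s01·x + s11·x² + σ²(residual).
- The four coefficient columns are 1, 2x, x² and 1. The first and last coincide, so the rank is 3 of 4 (2 of 3 without the covariance s01).
- Intercept and residual variance again cannot be separated. The slope terms can be estimated, but only as a variance that changes with dose. That weights the cohorts unequally and so can move β.

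**4. Size of the movement.** β from the random-slope REML fit was compared with least squares on simulated Part 1 data.

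| Fit | Data sets | Median abs. change in β | 95th percentile | SE ratio, 5th to 95th percentile |
|---|---|---|---|---|
| With covariance | 400 | 0.023 | 0.109 | 0.93 to 1.14 |
| Without covariance | 400 | 0.000 | 0.077 | 0.95 to 1.00 |

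A separate run of 300 data sets gave a median of 0.023 and a 95th percentile of 0.13. Against the half-width in step 2, 0.023 / 0.167 is about 14% and 0.109 / 0.167 about 65%. Over the assumed 8-fold dose range (40 / 5), the highest-to-lowest ratio changes by a factor of 8^0.023 = 1.05 at the median shift and 8^0.109 = 1.25 at the 95th percentile. Coverage of the 90% CI was 89% with covariance, against 90% for least squares. A standard mixed-model routine on the illustrative data set failed to converge and returned β = 0.926 instead of 0.945.

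**5. Degrees of freedom without the random terms.** Power model, N − 2: 24 − 2 = 22 (t = 1.717) and 18 − 2 = 16 (t = 1.746). One-way dose ANOVA, N − k: 24 − 4 = 20 and 18 − 3 = 15.

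**The case against.** The SAP foresees trouble: where random slopes cannot be fitted, it moves to a common slope, and that gives the least-squares β and SE. The average effect is also small, with a median shift near 0.02 and coverage of 89% against 90%. Protocol 9.4.1 leaves full statistical detail to the SAP. The study is unpowered, Protocol 9.1 plans no formal hypothesis testing, dose proportionality is not a listed objective, and Protocol 6.6 makes safety data the critical data for escalation.

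Most of this stands, and it limits the severity. It does not rescue the text. The fallback depends on the fit being impossible, and a random-slope fit can nominally converge with reweighted cohorts. Leaving detail to the SAP does not cover terms that the design cannot estimate.

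A reader might infer more than the documents support:
- *That the fallback itself can change β.* It cannot change β or its SE. Its sentence mentions only slopes, so whether a random intercept remains is itself an inference.
- *That the CI would be 3.7 times wider.* That needs about 1 df. No df method is stated, and nothing shows that 1 df would be used.
- *That the model has no fixed intercept because α is called random.* The displayed equation contains α and matches Protocol 9.4.4.1, so this is more likely loose wording.

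Two readings could supply more data per subject. If Part 2 Days 1 and 10 were pooled, each subject would have two values but still one dose level, and the Protocol synopsis says the days are separate. Part 1 bars recent trial medication (within 3 months) rather than naming earlier dosing in this study, but nothing plans re-entry at another dose.

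**Conclusion.** The concern holds, and the SAP is wrong as written. In every planned fit, the random subject effects in the power model and the dose ANOVA cannot be separated from residual error. That conclusion follows from the design and needs no assumption about the data.

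Only the first-choice random-slope model moves β. The illustrative shift is about 0.02 at the median and about 0.11 to 0.13 at the 95th percentile with covariance estimated, and smaller without it. These sizes rest on the assumed doses, the SD of 0.25 and the planned 24 subjects. The harm is an analysis that is not reproducible from its specification, rather than large average bias.

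The departure from Protocol 9.4.4.1 and the added ANOVA are undeclared in SAP section 2. This is a should-fix point: it affects the reported PK result, but not the primary safety objectives or any escalation decision.

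**What to change.** In SAP 7.12.3:
- State the power model as log10(y) = α + β·log10(dose) + error, with α a fixed intercept. Fit it by ordinary least squares with one row per subject and N − 2 df (22 in Part 1 and 16 in Part 2 at planned size). N is the number of subjects with a value for that endpoint.
- Fit the dose ANOVA as a fixed one-way model with N − k df, where k is the number of dose levels.
- Delete the random subject terms and the fallback sentence.

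List the added ANOVA in SAP section 2. With the random terms gone, the power model again matches Protocol 9.4.4.1 and needs no entry. Keep the random subject effect for the Part 3 crossover in SAP 7.12.4, where each subject receives both treatments.

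The cost is a few sentences in the SAP and simpler programming. No data collection changes.

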4.1.1. Part 1 (SAD)

Part 1 is a single ascending dose (SAD) study to assess the safety, tolerability and PK of single doses of ZP-059 in 4 cohorts of healthy male and female subjects. Each cohort will comprise 6 subjects (planned total of 24 subjects). An evaluable subject for Part 1 (SAD) of the study is defined as a subject who has received a dose of ZP-059 and has sufficient data for evaluation of the safety and PK objectives as outlined in $\frac{\text{Section 3.1.1}}{\text{Section 3.1.2}}$ and $\frac{\text{Section 3.1.2}}{\text{Section 3.1.2}}$, respectively.

An additional cohort of 6 subjects (Cohort 5) may be enrolled if it is deemed appropriate to repeat a dose level, assess an interim dose level or assess a dose level higher than planned (Section 6.6.1). Single doses will not exceed 40 mg of ZP-059 based on safety margins calculated following non-clinical studies (Section 4.3). For each dose escalation, the dose increase will not be more than 3-fold. A repeat dose level or higher dose level will only be assessed provided no dose escalation or study stopping criteria have been met.

Eligible subjects will receive a single dose of ZP-059 on the morning of Day 1. Subjects will be required to fast (water permitted) for at least 1 hour prior to each dose and 1 hour post each dose.

ZP-059 is a first in human IMP and therefore an additional safety precaution has been considered for dosing in each cohort and dose level for Parts 1 and 2. For the first 2 subjects in each cohort, there will be a minimum interval of 20 minutes between dosing. After the second subject is dosed there will be at least a 30 minutes observation period before the remaining 4 subjects are dosed. The remaining subjects will be dosed if the first two subjects show no clinically significant safety or tolerability concerns (including vital signs measurements, spirometry, physical examinations (symptom directed if required) and review of any adverse events [AEs] including any acute side effects e.g. excessive coughing) at the discretion of the investigator. Any clinically significant findings from the first two subjects in the opinion of the investigator will be discussed with the Sponsor prior to dosing of the remaining 4 subjects. The dosing interval between dosing subjects in the remainder of the cohort will be at the discretion of the investigator (in consultation with the sponsor if required) i.e. this could be increased or decreased as appropriate.

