The fixed starting dose for SAD Cohort 1 is 5 mg (1 x 5 mg capsule*) ZP-059 single dose administered via DPI (RS01 monodose device) on Day 1. *Capsule delivers 5 mg of voriconazole. Subsequent doses in the following cohorts will be determined from review of safety data from the preceding cohorts.

There will be an interim data review before each dose escalation to the next dose level to determine safety and tolerability. The time between cohorts will be sufficient to allow this review. Interim reviews will be based on safety data up to a minimum of 24 hours post-

dose for each dose level. Progression to the next dose level will only occur after a review of safety data from the previous dose level confirms that it is safe to do so. The interim decision meeting following SAD cohort 2 will also determine the dose to be administered in Part 2 MAD cohort 1. The data reviews will be conducted by the safety advisory committee (SAC), which will always comprise the Principal Investigator (or delegate) and the sponsor's medical monitor as a minimum (Section 6.6). Full details of interim data reviews, including dose escalation criteria, are provided in Sections 6.6.1 to 6.6.4.

Subjects will undergo safety, tolerability and PK evaluations at specified time points during the study (see Section 1.2). They will remain resident in the clinic until Day 2 after completion of safety assessments at 24 hours post-dose and providing there are no safety concerns, they will be discharged from the unit. A safety telephone call will be performed on Day 3 to check the status of unresolved AEs and to record any new AEs that have occurred after the last visit as well as any changes to concomitant medications. They will return to the clinic on Day 5 for safety evaluations to be performed. A safety follow-up call will be performed 8 to 12 days post dose to check the status of unresolved AEs and to record any new AEs that have occurred after the last visit as well as any changes to concomitant medications.

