# **Modification History**

Version	Change History	Reason	Date 12AUG2020
1.0	First Version	N/A	
2.0	
 
Update to protocol deviations listing to only important PDs
 
Removed exposure table from analysis
 
Updated AESI to tabulate if necessary
 
Added Sputum plug and processed sputum to analysis
 
	
 
To bring in line with SQN current processes
 
Following client review of dry run TFL
 
	280CT2020

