## 1 INTRODUCTION

This document details the statistical analysis that will be performed for the Zambon study: A Phase 1, Three-Part, Open-Label Study to Assess the Safety, Tolerability and Pharmacokinetics of Single Doses of Inhaled Voriconazole (ZP-059) in Healthy Subjects (Part 1), Multiple Doses of ZP-059 in Mild Stable Asthma Subjects (Part 2) and in a Two-Period Crossover Study of Single Doses of ZP-059 and Single Doses of Oral Voriconazole in Mild to Moderate Stable Asthma Subjects (Part 3).

The proposed analysis is based on the contents of the Final Version of the protocol (dated 13th December 2019), amendment 1 (dated 14th February 2020) and amendment 2 (dated 04 June 2020). In the event of future amendments to the protocol, this statistical analysis plan (SAP) may be modified to account for changes relevant to the statistical analysis.

The table, listing and figure shells are supplied in a separate document.

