#### 7.12.4 Bioavailability

The PK endpoints (see Section 7.12.3) estimated from Part 3 of the study will be analysed to assess relative bioavailability of Inhaled Voriconazole (ZP-059) to Oral Voriconazole (VFEND®) by fitting a mixed effects analysis of variance (ANOVA) model to the loge transformed PK parameter including fixed effect terms for treatment, period, sequence and sex and a random effect term for subject (nested within sequence). The adjusted geometric mean ratio (GMR) (Inhaled: Oral) and the corresponding 90% confidence interval (CI) for the adjusted GMR will be presented.

In addition, the PK endpoints will be compared between asthma subjects in Part 3 and healthy subjects in Part 1 and separately with asthma subjects in Part 2 to assess relative bioavailability of the Inhaled Voriconazole (ZP-059) dose taken in Part 3 in these populations. An ANOVA model will be fitted to the loge transformed PK

parameter including terms for the population group (i.e., healthy subjects or asthma subjects) and sex. The adjusted GMR and 90% CI for the adjusted GMR for the comparison between the two populations for the relevant dose will be provided, where the ratio is defined as either Part 3 subjects/Part 1 subjects or Part 3/Part 2 subjects, depending on the comparison.

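### The dose-proportionality ANOVA added in SAP 7.12.3 states no scale, dose-normalisation or null value; read literally, its p-value tests equal exposure, not proportional exposure

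*SAP*

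**What the plan says.** SAP 7.12.3 first sets out a power model on the log10 scale. A slope of 1 means perfect proportionality, and the slope with its 90% CI is the measure used. The section also back-transforms the modelled difference between the highest and lowest doses, and says that if exposure is proportional "there should be a fold increase equal to the ratio of highest: lowest dose across the dose range".

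It then adds a second method, an ANOVA: "A mixed effects model will be fitted with fixed effects for dose and random effects for subject". The stated output is: "The difference between the dose levels will be presented along with a 90% confidence interval and p-value". Read with the endpoint list just above it, this applies to Cmax, AUC0-t and AUC0-inf, for voriconazole and its N-oxide separately. No transformation, division by dose, null value, choice of dose pairs or rule for reading the result is given. Neither document mentions dose-normalised parameters anywhere.

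The next section is more explicit. SAP 7.12.4 fits its crossover ANOVA to the natural-log "transformed PK parameter including fixed effect terms for treatment, period, sequence and sex", and names a geometric mean ratio with a 90% CI as the result.

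Protocol 9.4.4.1 contains the power model only, and Protocol 9.1 says that no formal hypothesis tests are planned. On the outputs, SAP Section 1 says: "The table, listing and figure shells are supplied in a separate document".

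**The concern.** A p-value for a difference between the levels of a fixed factor tests, by default, whether that difference is zero. On un-normalised exposure, zero means that two doses give the same Cmax or AUC. That is not the hypothesis of proportionality, under which exposure should differ between doses by the dose ratio.

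Under a heading about dose proportionality, a small p-value invites the reading that exposure is not proportional, and a large one that it is. With a null of zero, both can be the wrong way round: a proportional drug is flagged, and a drug whose exposure does not rise with dose passes. The report could then carry an ANOVA p-value that appears to contradict a power-model slope close to 1.

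**Working it through.** The plan gives no power, alpha or variability figure for this analysis, so there is no figure to reproduce. The check is what the p-value would do if the text were followed literally.

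**1. Value implied by proportionality.** If exposure is proportional to dose, the log difference between two doses is log(dose ratio). For 40 v 5 mg this is ln(8) = 2.079; for 10 v 5 mg, ln(2) = 0.693; for 40 v 30 mg, ln(4/3) = 0.288. None is zero.

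**2. Inputs from the documents.** Six subjects per cohort and four cohorts in Part 1, with one dose per subject. The lowest dose is given: "The fixed starting dose for SAD Cohort 1 is 5 mg". The step limit is: "For each dose escalation, the dose increase will not be more than 3-fold". Single doses are capped at 40 mg. Later doses are not fixed, so 5/10/20/40, 5/15/30/40 and 5/10/15 mg are illustrative sets within those limits.

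**3. Assumptions.** Log-normal exposure; between-subject CV of 30, 50, 80 and 100% (the documents give none); p<0.05 (the SAP states no alpha); analysis on the log scale.

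**4. Formulas.** The log-scale SD is sqrt(ln(1+CV²)) = 0.294, 0.472, 0.703 and 0.833.

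- Pairwise difference: noncentral t with 4 × (6−1) = 20 df and noncentrality ln(ratio)/(SD × sqrt(2/6)). Example, 10 v 5 mg at CV 50%: 0.693/(0.472 × 0.577) = 2.54, against a critical value of 2.086, giving 68%.
- Overall F: noncentrality 6 × Σ(ln dose − mean)²/SD². Example, 5/10/20/40 mg at CV 100%: 6 × 2.402/0.693 = 20.8, giving 95%. For 5/10/15 mg at CV 100%: 6 × 0.617/0.693 = 5.34, giving 45%.

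**5. Results for an exactly proportional drug, un-normalised, n=6 per dose: percentage of trials with p<0.05**

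| Comparison | CV 30% | CV 50% | CV 80% | CV 100% |
|---|---|---|---|---|
| 10 v 5 mg (four doses) | 97 | 68 | 37 | 28 |
| 40 v 30 mg (four doses) | 37 | 17 | 10 | 9 |
| 40 v 5 mg (four doses) | 100 | 100 | 100 | 98 |
| Overall F, 5/10/20/40 mg | 100 | 100 | 99 | 95 |
| Overall F, 5/10/15 mg | 100 | 92 | 59 | 45 |

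**6. Same drug, dose-normalised.** log(parameter/dose) has the same mean at every dose, so the noncentrality is zero and each rate is the nominal 5%. Simulation of the overall F with 20,000 trials per setting gave 4.6-5.6%.

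**7. Flat exposure, 5/10/20/40 mg, n=6.** The un-normalised overall F is significant in about 5% of trials and the dose-normalised one in 95-100%. The un-normalised test thus passes the drug that fails proportionality.

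**8. The interval.** For the proportional drug, the un-normalised 90% CI for 40 v 5 mg on the log scale contains ln(8) in 90% of simulated trials and contains zero in under 1%. It is usable, but only against a benchmark that the SAP does not attach to it.

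**9. The scale.** For 10 v 5 mg at an assumed CV of 60%, in the 5/10/20/40 mg set with n=6, p<0.10 occurs in 67.8% of simulated trials on the log scale and 4.5% untransformed. The unstated scale can change the result.

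**The case against.** - **The SAP prints no null value.** Correct. Equal exposure is the default reading, not a written instruction. The shells may specify dose-normalisation, and outputs have been through a dry run: the Modification History gives one reason for the update as "Following client review of dry run TFL". A reader might infer that the trial will certainly run the wrong test; the documents do not show that. What they show is that the SAP, followed as it stands, leads there.
- **The log10 scale and the dose-ratio benchmark stand just above the ANOVA text.** The scale could reasonably be carried over. The benchmark is written for the power-model ratio, and nothing ties the ANOVA p-value to it.
- **The near-certain rejection rates come from the widest case.** This stands. A reader might take 95-100% as the general size, but that is an overall F-test across 5 to 40 mg. The SAP's stated output is differences between dose levels, where the rate can be as low as 9%.
- **There is no decision rule.** Protocol 9.1 plans no formal testing, and no conclusion is tied to this p-value. That limits the harm. It is also a reason to leave the p-value out.
- **The ANOVA is secondary.** This stands too. The slope with its 90% CI is already the stated measure.

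**Conclusion.** The point holds as a specification gap with a likely wrong target. SAP 7.12.3 does not say what its ANOVA p-value tests, and the literal reading tests equal exposure under a proportionality heading. For an exactly proportional drug, the un-normalised difference would be significant in roughly 9% to 100% of trials, depending on dose ratio and CV, against about 5% when dose-normalised. These figures rest on assumed CVs, assumed doses within the Part 1 limits, the log scale and a 0.05 cut-off. Part 2 doses are undetermined and are not illustrated.

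A reader might go further and conclude that the dose-proportionality assessment fails or that escalation is affected. The documents do not support either. The power-model slope remains valid, and Protocol 6.6 bases escalation on safety data. The cost is a supplementary output that may mislead or contradict the main one.

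**What to change.** In SAP 7.12.3, fit the ANOVA to loge(parameter/dose) with dose level as a fixed factor. Report ratios of dose-normalised geometric means with 90% CIs. Drop the p-value, which agrees with Protocol 9.1, or state that its null is a ratio of 1.

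Alternatively, delete the ANOVA and rely on the power-model slope with its 90% CI.

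The cost is SAP wording, plus updates to shells and programs if these are currently un-normalised. No extra data or subjects are needed.
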